Study information

Title	A pilot project to evaluate the feasibility of constructing a concurrent external control for recifercept		
Protocol number	C4181010		
Protocol version identifier	v 1.1		
Date	November 09, 2023		
EU Post Authorization Study (PAS) register number	N/A		
Active substance	Recifercept		
Medicinal product	N/A		
Research question and objectives	There are two research questions:		
	 Can a concurrent external control for the recifercept phase 2 clinical trial be constructed using achondroplasia patients from a prospective observational natural history study? What are differences in height growth, achondroplasia-related complications, patient functional status, and quality of life between patients enrolled in the recifercept phase 2 clinical trial and those in the concurrent external control? Objectives: 		
	 To construct a concurrent external control arm for recifercept phase 2 clinical trial using achondroplasia patients from a prospective observational natural history study. If objective #1 is met, the following will be compared to examine differences between patients enrolled in the recifercept phase 2 		
	clinical trial and those in the concurrent external control:		

PFIZER CONFIDENTIAL

CT24-WI-GL02-RF02 3.0 Non-Interventional Study Protocol Template For Secondary Data Collection Study 23-May-2022 Page 1 of 26

	Height growth
	• Selected anthropometric measurements, including but not limited to: standing height, sitting height, knee height, arm span, length of the legs, sitting height/standing height ratio, arm span to height/length difference, knee height/lower segment ratio
	 Achondroplasia-related orthopaedic complications (including lordosis, kyphosis, small foramen magnum, and spinal stenosis), and other achondroplasia-related complications (including apnea, otitis media, and hydrocephalus) Differences in functional status and health- related quality of life
Author	PPD

Recifercept C4181010 NON-INTERVENTIONAL STUDY PROTOCOL V1.1, Nov 09, 2023 1. TABLE OF CONTENTS	
1. TABLE OF CONTENTS	3
2. LIST OF ABBREVIATIONS	5
3. RESPONSIBLE PARTIES	6
4. ABSTRACT	7
5. AMENDMENTS AND UPDATES	13
6. MILESTONES	13
7. RATIONALE AND BACKGROUND	13
8. RESEARCH QUESTION AND OBJECTIVES	15

2. LIST OF ABBREVIATIONS

Abbreviation	Definition	
AE	Adverse event	
AOM	Acute otitis media	
BMI	Body mass index	
CCI		
СКД	Chronic kidney disease	
СОМ	Chronic otitis media	
CRF	Case report form	
CSA	Clinical study agreement	
DCT	Data collection tool	
EMA	European Medicines Agency	
FDA	U.S. Food and Drug Administration	
FGFR3	Fibroblast growth factor receptor 3	
GPP	Good Pharmacoepidemiology Practices	
ICH	International Council for Harmonisation	
IPW	Inverse probability weight	
MRI	Magnetic resonance imaging	
NPR-B	Natriuretic peptide receptor type B	
РК	Pharmacokinetics	
PS	Propensity score	
CCI		
SAP	Statistical analysis plan	

PFIZER CONFIDENTIAL CT24-WI-GL02-RF02 3.0 Non-Interventional Study Protocol Template For Secondary Data Collection Study 23-May-2022 Page 5 of 26

3. RESPONSIBLE PARTIES

Principal Investigator(s) of the Protocol

Name, degree(s)	Job Title	Affiliation	Address
PPD			

Recifercept C4181010 NON-INTERVENTIONAL STUDY PROTOCOL V1.1, Nov 09, 2023 **4. ABSTRACT**

Title: A pilot project to evaluate the feasibility of constructing a concurrent external control for recifercept

Version and Date: v1.1, November 09, 2023

Author: PPD

Rationale and background

Achondroplasia is a heritable autosomal dominant disorder and is the most common form of skeletal dysplasia in humans, with a global birth prevalence of 1 in 25,000-30,000 or approximately 250,000 individuals worldwide (1–3). Achondroplasia is caused by a single-point gain-of-function mutation in the gene encoding the fibroblast growth factor receptor 3 (FGFR3) (2,4). FGFR is a key inhibitory regulator of endochondrial ossification and its over-activitation interferes with normal chondrocyte maturation and causes shorter long bones and changes in flat bones such as the occipital bone and vertebrae.

Achondroplasia results in short stature and a range of severe complications due to abnormal ossification centers in the cranial base, facial bones, vertebrae, rib cage, and joints. Lordosis, kyphosis, small foramen magnum, and spinal stenosis are the most common achondroplasia-related orthopaedic complications. Other achondroplasia related complications include sleep-disordered breathing, otitis media, and hydrocephalus. Medical complications associated with achondroplasia greatly impact physical and psychosocial functioning, self-esteem, and patient quality of life (3,5).

Currently, vosoritide is the only treatment approved by European Medicines Agency (EMA) (for achondroplasia patients aged 2 years and older with open growth plates) and U.S. Food and Drug Administration (FDA) (for achondroplasia patients aged 5 years and older with open growth plates) to increase linear growth. It is an analog of C-type natriuretic peptide and works by binding to a receptor called natriuretic peptide receptor type B (NPR-B), which reduces the activity of FGFR3. Other available treatments are either aimed at limb lengthening with surgery or are interventions to treat the complications associated with achondroplasia. Recifercept is a modified soluble recombinant human FSFR3 under development for the treatment of achondroplasia. Recifercept is designed to be a decoy protein, competing for ligands of the FGFR3-G380R receptor responsible for achondroplasia and by forming inactive heterodimers with FGFR3 monomers. By binding free FGFR3-activating ligands and forming inactive dimers, recifercept reduces activation of the receptor, allowing chondrocyte proliferation and differentiation to proceed.

A recifercept phase 2 clinical study (Study C4181005) is ongoing to investigate the safety, tolerability, pharmacokinetics (PK) and efficacy of recifercept in children aged 3 months to 10 years with achondroplasia. Fifty-four eligible participants aged 2-10 years and 9 patients aged 3 months to 2 years will be enrolled and randomized to receive one of three doses of

PFIZER CONFIDENTIAL

recifercept subcutaneously (1mg/kg once-weekly, 2mg/kg twice weekly, or 1.5mg/kg oncedaily, n=21 per dose). Once participants complete the phase 2 trial, they will be offered enrollment into an open-label extension study at the dose previously received in the phase 2 trial or at the therapeutic dose once it is identified. A separate multi-country prospective observational natural history study (Study C4181001) is ongoing to examine the anthropometric characteristics, achondroplasia-related symptoms, tests, and treatments among children with achondroplasia. A total of 300 achondroplasia patients aged 0 to 15 years of age will be recruited and followed up for a duration of 5 years. All patients participating in Study C4181005 were or will be recruited from Study C4181001.

Objectives of this project are to evaluate the feasibility of constructing a concurrent external control for the recifercept phase 2 clinical trial (Study C4181005) using achondroplasia patients from the ongoing prospective natural history study (Study C4181001) and to compare selected outcomes of interest such as height growth, achondroplasia-related complications, patient functional status, and quality of life between achondroplasia patients in Study C4181005 and those in the concurrent external control. Ultimately, this project will assess the feasibility of leveraging the ongoing Study 4181001 to construct a concurrent external control for the recifercept pivotal trial.

Research question and objectives

There are two research questions:

1) Can a concurrent external control for the recifercept phase 2 clinical trial be constructed using achondroplasia patients from a prospective observational natural history study?

2) What are differences in height growth, achondroplasia-related complications, patient functional status, and quality of life between patients enrolled in the recifercept phase 2 clinical trial and those in the concurrent external control?

Objectives of this pilot project will be:

- 1. Construct a concurrent external control arm for recifercept phase 2 clincial trial using achondroplasia patients from a prospective observal natural history study
- 2. If objective #1 is met, the following will be compared to examine differences between patients enrolled in the recifercept phase 2 clincial trial and those in the concurrent external control:
 - Height growth
 - Selected anthropometric measurements, including but not limited to: standing height, sitting height, knee height, arm span, length of the legs, sitting height/standing height ratio, arm span to height/length difference, knee height/lower segment ratio

PFIZER CONFIDENTIAL

- Achondroplasia-related orthopaedic complications (including lordosis, kyphosis, small foramen magnum, spinal stenosis), and other achondroplasia-related complications (including apnea, AOM, and hydrocephalus)
- Differences in functional status and health-related quality of life

Study design

This is a retrospective cohort study using existing data from two ongoing studies: C4181001 and C4181005. Study C4181005 includes 63 achondroplasia patients in total, approximately 54 patients aged 2 to 10 years (inclusive) and 9 patients aged 3 months to 2 years, who are enrolled and randomized to receive one of three doses of recifercept (1mg/kg once-weekly, 2mg/kg twice-weekly, or 1.5mg/kg once-daily, n=21 per dose) subcutaneously for 12 months. Study C4181001 includes approximately 300 children with achondroplasia aged 0-15 years who are recruited from global sites. Patient data will be collected at baseline and at every 3-month interval visit, for a maximum of 5 years.

Study population

Inclusion Criteria:

All patients from Study C4181005 who have completed Visits 1 through 11 (at D183) will be included in this project.

To construct a concurrent external control from Study C4181001, patients from Study C4181001 will need to meet the following eligibility criteria from Study C4181005:

- Documented, confirmed genetic diagnosis of achondroplasia from historical medical records (test must have been performed at a laboratory fully accredited for genetic testing under local regulations)
- Aged ≥ 3 months to <11 years (up to the day before 11th birthday inclusive) at time of enrollment into Study C4181001
- Have completed at least 2 valid height/length measurements (at least 3 months apart)
- Assessed for Tanner stage 1 during physical examination before or at enrollment into Study C4181001 (must include assessment of breast development for females, or testicular stage for males)
- Able to stand independently for height measurements (if ≥ 2 years of age at enrollment); If aged <2 years at enrollment, has a documented historical MRI brain/cervical spine performed in the previous 12 months.
- Have at least 6 months of available follow-up data after enrollment into Study C4181001

PFIZER CONFIDENTIAL

CT24-WI-GL02-RF02 3.0 Non-Interventional Study Protocol Template For Secondary Data Collection Study 23-May-2022 Page 9 of 26 Recifercept C4181010 NON-INTERVENTIONAL STUDY PROTOCOL V1.1, Nov 09, 2023 Exclusion criteria:

- Presence of severe obesity (BMI > 95% percentile on Hoover-Fong BMI charts)
- Body weight <7kg or >30kg
- History of chronic kidney disease (CKD) or renal impairment
- History of receipt of any treatment that are known to potentially affect growth (including oral steroids > 5 days in the last 6 months before enrollment, high dose inhaled corticosteroids (>800 mcg/day beclametasone equivalent) and medication for attention deficient hyperactivity disorder)
- Less than 6 months since fracture or surgical procedure of any bone determined from the baseline visit date.
- Presence of any internal guided growth plates/devices

History of removal of internal guided growth plates/devices within 6 months prior to enrollment

Data sources

This retrospective cohort study will include achondroplasia patients from Study C4181005 and those from Study C4181001 who meet the inclusion and exclusion criteria of Study C4181005. Study C4181005 is a single-arm trial to evaluate the safety and tolerability of recifercept doses and dosing regimen, and efficacy to increase height growth in achondroplasia patients. Study C4181005 will include approximately 63 children with achondroplasia aged 3 months to 10 years (inclusive) with Tanner Stage 1, who are enrolled and randomized to receive one of three doses of recifercept (1mg/kg once-weekly, 2mg/kg twice-weekly, or 1.5mg/kg once-daily) subcutaneously for 12 months. Demographics, medical history, anthropometric measurements, and patient-reported outcomes in functional status and quality of life are collected approximately every 3 months. Study C4181001 is a prospective natural history study to collect longitudinal anthropometric and disease-related complication data in children with achondroplasia. It will include approximately 300 achondroplasia patients aged 0-15 years with Tanner Stage 1 recruited from global sites. Patient data will be collected at baseline and at every 3-month interval visits, for a maximum of 5 years. Further details on data sources are presented in Table3.

Study size

The determination of study size of this protocol is exclusively limited to addressing the second objective of examining the differences between patients enrolled in the recifercept phase 2 clinical trial and those enrolled in the concurrent external control. For the purposeof consistency with the analysis of the primary endpoint Study C4181005, consideration of study size for this protocol is further limited to a comparison of height growth, defined as the

PFIZER CONFIDENTIAL

CT24-WI-GL02-RF02 3.0 Non-Interventional Study Protocol Template For Secondary Data Collection Study 23-May-2022 Page 10 of 26

ratio of change from baseline of standing height at 6 months or 12 months of a patient taking recifercept to a matched subject in the concurrent external control. The null hypothesis is the median value (ie, 50 percentile) of the aforementioned ratio is equal to 1.

A table and figure presented below displays the number of pairs required to detect the median ratio (denoted as φ) under the alternative hypothesis.

Type I error	Power	Number of Pairs to detect φ					
		φ=1.5	$\phi = 2$	φ=2.5	$\phi = 3$	φ=3.5	$\phi = 4$
.05	.8	88	22	10	6	4	3
.05	.9	115	29	13	8	5	4
.1	.8	71	18	8	5	3	2
.1	.9	96	24	11	6	4	3
.2	.8	55	14	7	4	3	2
.2	.9	77	20	9	5	4	3

Table 1. Sample size and power calculation

Data analysis

Descriptive statistics will be tabulated on patient demographic and baseline clinical characteristics between achondroplasia patients from Study C4181005 and patients from Study C4181001 who meet all the inclusion and exclusion criteria of Study C4181005. To construct a concurrent external control for Study C4181005, a propensity score (PS) will be created to achieve balance across covariates between achondroplasia patients from Study C4181005 and patients from Study C4181001 who meet all the eligibility criteria of Study C4181005. The PS will be estimated using standard logistic regression approaches with the "outcome" variable being the data source (whether patients were included in Study C4181005 and exposure to recifercept treatment) and the predictors being the variables associated with both the exposure (recifercept treatment) and the outcomes of interest (i.e. height growth). This model will provide the predicted probability of being in the trial cohort relative to the concurrent external control cohort as a function of the covariates (the propensity score of being included in Study C4181005). The potential covariates may include demographics (e.g. age, gender, race and ethnicity), clinical characteristics (e.g. presence of achondraplasia-related complications, Tanner stage, and other non-achondroplasia-related conditions of medical significance). The distribution of the PS will be reviewed and patients with a PS in the areas of nonoverlap and/or with extreme PS values might be excluded to improve validity (PS trimming). Each patient in the PS trimmed receifercept group will be

PFIZER CONFIDENTIAL

CT24-WI-GL02-RF02 3.0 Non-Interventional Study Protocol Template For Secondary Data Collection Study 23-May-2022 Page 11 of 26

matched on a ratio of 1:1 with patients in the PS trimmed concurrent external control using optimal nearest neighbour matching with a maximum caliper of 1%. Pre- and post-matching balance will be assessed using standardized differences between these two PS-matched groups. A negative control outcome may also be identified to evaluate the pre- and post-matching balance.

After the concurrent external control is constructed by PS matching, descriptive statistics will be tabulated on patient demographic and baseline clinical characteristics between achondroplasia patients from PS-matched recifercept phase 2 trial cohort and those from PS-matched concurrent external control. Two-sample T-tests will be used for continuous variables, and chi-square tests for categorical variables assuming the distribution is normal. Frequency of primary, secondary **CC** outcomes of interest and 95% confidence intervals will be computed.

Hazard ratios and associated 95% confidence intervals of dichotomous outcomes (including height growth in the achondroplasia reference population +50%, and occurrence of selected achondroplasia-related complications) in PS-matched groups will be estimated by multivariable cox proportional hazards regression models. The effect of recifercept on continuous outcomes (including height growth, anthropometric measures, CCL

in PS-matched groups will be estimated by linear mixed

models.

To maximize the number of patients in the trial cohort and the concurrent external control cohort included in this pilot project, additional methods will be explored. Coarsened weighting and full matching may be explored. Other than matching, inverse probability weight (IPW) and/or the fine stratification weighting may also be used to balance the key covariates between patients in the concurrent external control cohort (patients in C4181001 who meet the inclusion and exclusion criteria of Study C4181005) and patients in Study C4181005 (details of these methods will be outlined in the SAP).

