9.6. Data analysis

A single pooled dataset will be released for analysis. The release will occur when for selected, targeted data (in Table 3): a) review and documentation of relevant CRF and non-CRF data; and b) all open queries are resolved. There will be two releases of data. The first release coincides with approximately 30 pairs of patients – that is, a patient from C4181001 matched to a patient from C4181005 – having 6 months of growth data. The second release will take place at the beginning of the interim analysis for C4181005. There may be an additional release of data from both studies that coincides with the completion of C4181005.

Descriptive statistics will be tabulated on patient demographic and baseline clinical characteristics between achondroplasia patients from Study C4181005 and patients from Study C4181001 who meet all the inclusion and exclusion criteria of Study C4181005. To construct a concurrent external control for Study C4181005, a propensity score (PS) will be created to achieve balance across covariates between achondroplasia patients from Study C4181005 and patients from Study C4181001 who meet all the eligibility criteria of Study C4181005. The PS will be estimated using standard logistic regression approaches with the "outcome" variable being the data source (whether patients were included in Study C4181005 and exposure to recifercept treatment) and the predictors being the variables associated with both the exposure (recifercept treatment) and the outcomes of interest (i.e. height growth). This model will provide the predicted probability of being in the trial cohort relative to the concurrent external control cohort as a function of the covariates (the propensity score of being included in Study C4181005). The potential covariates may include demographics (e.g. age, gender, race and ethnicity), clinical characteristics (e.g. presence of achondraplasia-related complications, Tanner stage, and other nonachondroplasia-related conditions of medical significance). The distribution of the PS will be reviewed and patients with a PS in the areas of nonoverlap and/or with extreme PS values might be excluded to improve validity (PS trimming). Each patient in the PS trimmed receifercept group will be matched on a ratio of 1:1 with patients in the PS trimmed concurrent external control using optimal nearest neighbour matching with a maximum

PFIZER CONFIDENTIAL

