9.7. Data sources

For this pilot study, the data in Table 9.3 from C4181001 and C4181005 will be pooled to create a single dataset. With respect to patients the component datasets will be mutually exclusive – that is, there are no patients common to both studies.

This retrospective cohort external control arm study will include achondroplasia patients from Study C4181005 and those from Study C4181001 who meet the inclusion and exclusion criteria of Study C4181005. Study C4181005 is a single-arm trial to evaluate the safety and tolerability of recifercept doses and dosing regimen, and efficacy to increase height growth in achondroplasia patients. Study C4181005 will include approximately 63 children with achondroplasia aged 3 months to 10 years (inclusive) with Tanner Stage 1, who are enrolled and randomized to receive one of three doses of recifercept (1mg/kg onceweekly, 2mg/kg twice-weekly, or 1.5mg/kg once-daily) subcutaneously for 12 months. Demographics, medical history, anthropometric measurements, and patient-reported outcomes in functional status and quality of life are collected approximately every 3 months. Study C4181001 is a prospective natural history study to collect the longitudinal anthropometric and disease-related complication data in children with achondroplais. It will

PFIZER CONFIDENTIAL

CT24-WI-GL02-RF02 3.0 Non-Interventional Study Protocol Template For Secondary Data Collection Study 23-May-2022 Page 23 of 26 Recifercept C4181010 NON-INTERVENTIONAL STUDY PROTOCOL V1.1, Nov 09, 2023 include approximately 300 achondroplasia patients aged 0-15 years with Tanner Stage I recruited from global sites. Patient data will be collected at baseline and at every 3-month interval visits, for a maximum of 5 years. Further details on data sources are presented in Table 2.

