CT24-WI-GL03-RF03 2.0 Non-Interventional Statistical Analysis Plan For Secondary Data Collection Study 01-Jun-2020 Page 11 of 17 related conditions of medical significance). The distribution of the PS will be reviewed and patients with a PS in the areas of nonoverlap and/or with extreme PS values might be excluded to improve validity (PS trimming). Each patient in the PS trimmed receifercept group will be matched on a ratio of 1:1 with patients in the PS trimmed concurrent external control using optimal nearest neighbour matching with a maximum caliper of 1%. Pre- and post-matching balance will be assessed using standardized differences between these two PS-matched groups. A negative control outcome may also be identified to evaluate the pre- and post-matching balance. There are different options that will be considered while modelling via PS. These include:

- 1. Calipers: range from [.01,.25]
- 2. Statistic (used to match treated to control subject): logit of PS, minimizing difference of PS, Mahalanobis distance
- 3. Ratio match (treatment-to-untreated): 1-to-1, 1-to-m

Exact matching can be included within the PS model. Exact matching will be done by gender. A binary variable will be created to specify race. The variable will have the value of "Yes" for "White" and "No" for all other values.

Standardized mean differences of the matched variables are the main criteria used to determine whether objective 1 is met. An external control dataset is confirmed (i.e., objective 1 is met) when all of the standard mean differences for the matched variables are less than 0.1.

After the concurrent external control is constructed by PS matching, descriptive statistics will be tabulated on patient demographic and baseline clinical characteristics between achondroplasia patients from PS-matched recifercept phase 2 trial cohort and those from PS-matched concurrent external control. Two-sample T-tests will be used for continuous variables, and chi-square tests for categorical variables assuming the distribution is normal. Frequency of primary, secondary and exploretary outcomes of interest and 95% confidence intervals will be computed.

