7.2.4 Summary of Analyses

The list below is not an exhaustive list of statistical analyses that will be performed for objective 1.

Outcome	Analysis Set	Supports Protocol Objective Number	Subgroup	Statistical Method	Covariates/Strata	Missing Data
External Control dataset	Full analysis set	1	None	Propensity score matching or IPW via Logistic regression	Demographic and clinical characteristics, including baseline comorbidities.	Excluded
Height Z-Score (and other Anthropometric endpoints)	Full analysis set	2	None	Mixed model repeated measures model, Propensity Score Matched or IPW	Propensity Score Matched, or data augmented by IPW, by Demographic and clinical characteristics.	Excluded

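### Objective 1's all-SMDs-below-0.1 rule has no stated operating characteristics; with at most 63 treated children, its answer depends almost wholly on a covariate list and method that the plan leaves open

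*Protocol*

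**What the plan says.** Protocol section 4 (Study size), repeated in 9.4, states: "The determination of study size of this protocol is exclusively limited to addressing the second objective". Its Table 1 gives numbers of pairs for a median height-growth ratio only.

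SAP 7.2.1 confirms the external control, and so meets Objective 1, "when all of the standard mean differences for the matched variables are less than 0.1". SAP 2.2 and 7.2.2 make Objective 2 conditional on this. Neither document says how often a comparable control set would pass, or a non-comparable one fail.

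The variables to which the rule applies are not fixed:

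- Protocol 9.6 and SAP 7.2.1 give an open list of possible covariates.
- Protocol Table 3 gives the covariate role to age, gender, race and ethnicity, Tanner stage, weight and six condition histories.
- SAP 7.2.4 describes the covariates as "Demographic and clinical characteristics, including baseline comorbidities".
- The only concrete propensity model, in SAP 10.3, has three variables: SEX, AAGE and WHITE.

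The method is not fixed either:

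- SAP 7.2.1 sets a 1% caliper, then lists calipers from .01 to .25, three distance statistics and 1:1 or 1:m matching.
- SAP 7.2.2 requires 1:1 for the matched analysis; the code in 10.3 matches at a variable ratio of up to 4.
- IPW is offered as another route. There, standardized differences under 10% may be regarded as negligible, but this is not written as the Objective 1 rule.

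**The concern.** Objective 1 is the study's first research question, and its answer is meant to inform use of the natural history study as a control for a pivotal trial. A decision rule for it should usually pass a comparable control set and usually fail one that is not. At 63 pairs or fewer, a limit of 0.1 lies inside the chance variation of a single standardized difference, and the rule requires every variable to pass.

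A long list under 1:1 matching therefore makes failure nearly certain. A short list with exact matching makes success nearly certain, while covariates the protocol itself names go unchecked. In either case a reader could take the result as evidence on feasibility when it mainly reflects the choice of list and method.

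**Working it through.** **1. The plan's own figure.** All 36 cells of Table 1 are reproduced by n = ceil[(π²/4)(z(1−α/3) + z(power))²/(φ−1)²], the large-sample variance of a Cauchy median with a one-sided test at α/3. For α = .05 and power .8: (2.128 + 0.842)² × 2.467 = 21.76. This gives 22 pairs at φ = 2, and 21.76/0.25 = 87.04, so 88 pairs, at φ = 1.5. The α/3 is inferred, not stated. The table is sound on its own terms but says nothing about Objective 1.

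**2. Inputs.**

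- Treated: "Study C4181005 includes 63 achondroplasia patients in total" (Protocol section 4). This caps the 1:1 pairs, before losses to the D183 completion rule, trimming and caliper.
- Pool: "A total of 300 achondroplasia patients aged 0 to 15 years of age will be recruited" (Protocol section 4), and "there are no patients common to both studies" (Protocol 9.7). If the 63 trial children come out of the 300, at most 300 − 63 = 237 controls remain before eligibility. Assumed range: 120-237.
- Covariates: age, sex, White yes/no, weight and six histories, about ten. Tanner stage is constant at 1.
- Assumed: history prevalences of about 5-40% (up to 50% in some runs), independent conditions, weight correlated with age.

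**3. Chance benchmark (two random samples, no matching).** SE of an SMD = sqrt(2/n) = sqrt(2/63) = 0.178. P(|SMD| < 0.1) = 2Φ(0.1/0.178) − 1 = 0.425. If the variables are independent, all pass with probability 0.425³ = 0.077 for three and 0.425¹⁰ = 0.0002 for ten. For a yes/no variable at 10% prevalence, the limit is 0.1 × sqrt(0.1 × 0.9) × 63 = 1.9, so the groups may differ by one child. Matching reduces this noise, so simulation is needed.

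**4. Simulation.** Logistic propensity score, optimal 1:1 matching or IPW, 63 treated, mostly 250-600 runs per setting. With 300 runs the Monte Carlo SE is about sqrt(.05 × .95/300) = 1.3 points at 5%, and sqrt(.8 × .2/300) = 2.3 points at 80%. Ranges span the settings tried.

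| Variables and method | Identical pool passes | Poor pool passes |
|---|---|---|
| Ten, one 1:1 match | 2-8% | 2-12% |
| Ten, best of the caliper and distance options tried | about 20-28% | not reported |
| Three coded, 1:1, exact on sex and White | 99-100% | 99.8-100% (all covariates shifted 0.5 SD) |
| Three coded, 1:1, exact on sex only | 78-85% | not reported |
| Three coded, approximate variable ratio up to 4, unweighted SMDs | about 53% | not reported |
| Ten, IPW | 72-93% | 3-10% (complications about 12.5 points more common); 26% at 0.25 SD; 0% at 0.5 SD |
| Three coded, IPW | about 99% | 92-94% at 0.25 SD; 28-34% at 0.5 SD |

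**5. What the three-variable match leaves unchecked.** In one setting, the largest SMD among weight and the six histories had a median of 0.28 with an identical pool and 0.52 with complications 12 points more common. Both pools passed every time.

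**6. Number treated.** For an identical pool, ten-covariate IPW passes 44-48% at 45 treated and 9-11% at 30. One 1:1 ten-covariate match would need far more treated children than exist: it passes 52% at 200 and 93% at 500.

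**The case against.** The strongest reply is that the SAP nowhere fixes a ten-covariate match. Its lists are open, and its one concrete model has three variables. That is right, and the 92-98% rejection rate belongs only to a single 1:1 match on about ten covariates. But Table 3 and SAP 7.2.4 point to that longer list, so text and code lead to opposite, near-certain answers.

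Second, the plan already offers IPW, and IPW discriminates. This stands and shapes the fix. It does not close the gap: the rule in 7.2.1 is worded for matched variables, IPW over the three coded variables still leaves weight and histories unchecked, and no pass probability is given.

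Third, an SMD describes the sample obtained. Chance imbalance is real imbalance, and matching exists to repair a poor pool, so equal pass rates for good and poor pools are not by themselves a fault. This is fair. Yet the ten-covariate match seldom passes in either case, and sets passed on three variables are themselves imbalanced on the others.

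Fourth, "The first release coincides with approximately 30 pairs of patients" (Protocol 9.6) describes a data release. A reader might infer that Objective 1 is to be decided at 30 pairs. The documents do not say so, and results at that size are background only.

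**Conclusion.** The point holds in this form: with at most 63 treated children and no stated operating characteristics, the Objective 1 result depends almost wholly on the covariate list and method, and the plan fixes neither. One 1:1 match on about ten covariates rejects about 92-98% of identical pools. The coded three variables matched 1:1 pass almost always, in good and poor pools alike. IPW over the ten covariates is informative at 63 treated and clearly weaker at 45.

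Three stronger readings are tempting and not supported:

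- That the study would almost surely report that a control is not feasible. Under the coded variables matched 1:1, the opposite is expected.
- That the 0.1 rule cannot discriminate under any method. Under IPW it does.
- That the study is too small and should be larger. It uses existing data, the number treated is capped, and the remedy is specification.

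The rates rest on assumed prevalences, independent conditions and pool size. The contrast between the methods was consistent across the settings tried; the exact percentages should be recomputed on the actual covariates.

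**What to change.** In SAP 7.2.1 and 10.3:

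- Put the Table 3 baseline covariates that vary (age, sex, race, weight, six histories) in both the propensity model and the balance check, in place of the three coded variables.
- Decide Objective 1 on the propensity-weighted SMDs already planned in 7.2.1, together with a prespecified minimum effective number of controls, (Σw)²/Σw². One natural floor is the number of treated children analysed. Keep 1:1 matching as a sensitivity analysis.
- Include any covariate with residual imbalance in the Objective 2 model. SAP 7.2 names age and gender as fixed effects, but SAP 5.4 lists no covariates and the 10.3 models contain neither, so these need to be aligned as well.
- State the simulated pass probability for comparable and non-comparable pools at the achievable number treated, for example 45 and 63. This uses covariates only and can be done before any outcome is analysed.

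Two alternatives should not be the sole criterion. Entropy-balancing weights meet the 0.1 rule by construction: they passed 99.7-100% of poor pools, and only the effective number of controls revealed the problem (about 139 of 174 falling to 38). Relaxing the limit to 0.25 under 1:1 matching passed good and poor pools alike (91% against 87-90%).

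The cost is SAP wording and some extra programming, with no new data. The downside is a smaller effective number of controls, which must be reported.
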